10. SAFETY ANALYSES

All safety analyses will be conducted using the SP unless specified otherwise below. All safety analyses will be completed using the actual treatment a subject received. Observed case data will be used; no imputation will be performed for missing safety data except for the limited situations described in Section 7.3.2.

All safety data will be presented in by-subject listings. Unscheduled assessments will not be summarized but will be included in the listings.

10.1. Adverse Events

AEs will be coded using MedDRA, Version 23.1.

Treatment-emergent adverse events (TEAEs) are defined as any AE that begins or worsens after initiation of the investigational product and through the subject's last study visit (study completion or early termination).

If the onset of an AE is on or after the date of first dose of study medication or is increasing in severity after first dose of study medication, then the AE will be considered treatment emergent.

Only TEAEs will be summarized; all AEs (TEAE, non-TEAE) will be included in a by-subject listing.

The number and percent of subjects with any TEAEs will be summarized by SOC and PT by treatment group and overall. At each level of tabulation (e.g., at the PT level), subjects will be counted only once if they had more than one such event reported during the AE collection period.

Note that in MedDRA, ocular events are coded to the SOC of "Eye Disorders". Thus, using SOC in the summaries will provide a separation of ocular and non-ocular adverse events.

The following summary tables will be presented for TEAE data:

- Overall summary of TEAEs (completed for both the SP and mITT population)
- Summary table of TEAEs by SOC and PT
- Summary table of TEAEs by SOC, PT, and by greatest relationship level to study drug (not related, unlikely related, possibly related, probably related, definitely related, or unknown)
- Summary table of TEAEs by SOC, PT, and maximum severity (mild, moderate, severe)
- Summary table of serious TEAEs by SOC and PT
- Summary table of TEAEs leading to withdrawal from the study by SOC and PT

- Summary table of TEAEs leading to study medication discontinuation by SOC and PT

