Regarding safety, Nyxol 1% was well tolerated and there were no major ocular or systemic safety issues. An evening dose regimen minimized eye redness during the daytime while benefiting near VA in an elderly population. The incidence of treatment-emergent adverse events (TEAEs) was higher in the Nyxol arm compared with the placebo arm (31.6% versus 5.0%) but all TEAEs were mild in severity, with no serious TEAEs or TEAEs leading to withdrawal or study medication discontinuation. Most TEAEs were considered related to study medication, with the most frequent being conjunctival hyperemia and burning on instillation (each seen in 16% of subjects treated with Nyxol). Although conjunctival redness scores increased in the Nyxol arm at Day 8, Day 15, and Day 16, the scores in the Nyxol arm at any post-baseline timepoint did not demonstrate a statistically significant difference from scores in the placebo arm. Mean systolic and diastolic BPs and HRs were relatively unchanged and remained within normal range throughout the duration of the trial and were similar between arms. Neither biomicroscopic nor ophthalmoscopic examination showed any clinically significant abnormalities at Screening or at Day 15. There was no worsening of distance VA, near VA, or IOP.

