4.1. Study Objectives

The objectives of this study are as follows:

Primary objective

- To evaluate the efficacy of Nyxol + LDP to improve distance-corrected near visual acuity (DCNVA) compared to Placebo alone in subjects with presbyopia

Secondary objectives

- To evaluate the efficacy of Nyxol + LDP to prevent >1 line of loss of best-corrected distance visual acuity (BCDVA)
- To evaluate the efficacy of Nyxol + LDP to improve DCNVA compared to Nyxol alone or LDP alone
- To evaluate the ability of Nyxol + LDP to produce the “pinhole” pupil size (approximately 1.6-2 mm)
- To evaluate the efficacy of Nyxol + LDP to improve distance-corrected intermediate visual acuity (DCIVA) and BCDVA
- To evaluate the effect of iris color on the efficacy of Nyxol + LDP
- To evaluate the ocular and systemic safety of Nyxol + LDP and each component individually

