6. SAMPLE SIZE

A sample size of approximately 140 subjects (40 for Nyxol + LDP and Placebo alone arms and 30 for each of the other 2 arms) who are evaluable for efficacy is needed for the study. The primary treatment comparison will be Nyxol + LDP compared to Placebo alone.

Subjects will be randomized 4:3:3:4 to Nyxol + LDP, Nyxol + No Treatment 2 (Nyxol alone), Placebo + LDP, and Placebo + No Treatment 2 (Placebo alone), respectively.

It is assumed that there will be approximately 7% drop-out between Visit 1 and end of Visit 2. To account for this drop-out, a total of approximately 152 subjects will be randomized into the study.

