7.4. Planned Study Analyses

7.4.1. Statistical Summaries: Descriptive and Inferential

Categories for data presentation and analysis will consist of each treatment group: Nyxol + LDP, Nyxol + No Treatment 2 (Nyxol alone), Placebo + LDP, Placebo + No Treatment 2 (Placebo alone).

All statistical tests will be two-sided and a difference resulting in a p-value of less than or equal to 0.05 will be considered statistically significant. The p-values for the analysis of secondary efficacy endpoints and safety endpoints will be considered descriptive. All p-values will be rounded to and displayed in four decimals. If a p-value less than 0.0001 occurs, it will be shown in tables as <0.0001.

Descriptive summaries of variables will be provided where appropriate. For continuous variables, the number of non-missing values (n), mean, standard deviation, median, minimum, and maximum will be tabulated by treatment group. For categorical variables, the counts and proportions of each value will be tabulated by treatment group. Expansion of descriptive table categories within each treatment may occur if such elaborations are thought to be useful.

All study-related data collected will be presented in listings. Study-related data not subject to analysis according to this plan will not appear in any tables or graphs but will be included in the data listings.

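### TEAEs are tabulated over one whole-study window by four arms, so events before Treatment 2 in subjects who later receive LDP fall in LDP columns, and no listed table pools Nyxol against Placebo for that period

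*SAP*

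**What the plan says.** SAP Section 10.1 defines a TEAE as an event that starts or worsens between the first study medication and the subject's last visit. The main tabulation reads: "The number and percent of subjects with any TEAEs will be summarized by SOC and PT by treatment group and overall". A subject counts once per term over the whole collection period. Severity is shown at its maximum and relationship at its greatest level to study drug, without separating Treatment 1 from Treatment 2. Seven TEAE tables are listed; none is split at Treatment 2 and none pools arms by Treatment 1. Section 7.4.1 sets the display groups: "Categories for data presentation and analysis will consist of each treatment group: Nyxol + LDP, Nyxol + No Treatment 2 (Nyxol alone", followed by the two Placebo arms. Protocol Section 9.3.6 adds no split by period.

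Protocol Sections 2.1 and 6.1 give the sequence: Nyxol or Placebo in the evening for 3 to 4 days, then LDP or nothing at Time 0 of Visit 2.

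One secondary objective in SAP Section 4.1 is "To evaluate the ocular and systemic safety of Nyxol + LDP and each component individually". For efficacy, Section 4.2.2 compares Nyxol-treated with Placebo-treated subjects on photopic DCNVA at Visit 2, 0 minutes, before Treatment 2. Sections 10.3 to 10.6 summarise hyperemia, tolerability, vital signs and IOP at 0 minutes by treatment group. TEAEs have no equivalent summary.

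**The concern.** Until Time 0 of Visit 2 the two Nyxol arms have had the same treatment, and so have the two Placebo arms. An event in that interval cannot be due to LDP. In a subject who later receives LDP, it is nevertheless counted under Nyxol + LDP or Placebo + LDP. Because each subject counts once per term, redness on Nyxol and again after LDP is a single count, and the table does not show which came first.

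Two things are at stake. One is attribution: the expected effects overlap (hyperemia and burning on instillation for Nyxol, stinging and browache for pilocarpine, Protocol Section 2.2), so timing helps to separate the components. The other is precision on Nyxol's own AE rate, for which the whole randomised sample is available before Treatment 2.

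**Working it through.** **Inputs.** SAP Section 6: allocation ("Subjects will be randomized 4:3:3:4 to Nyxol + LDP", then the other three arms), evaluable numbers ("40 for Nyxol + LDP and Placebo alone arms and 30 for each of the other 2 arms"), drop-out ("It is assumed that there will be approximately 7% drop-out between Visit 1 and end of Visit 2") and total ("a total of approximately 152 subjects will be randomized into the study"). Illustrative TEAE rates, Protocol Section 2.2: 31.6% on Nyxol and 5.0% on placebo in a 14-day trial with 19 and 20 subjects. All other rates below are assumptions.

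**The plan's own figure.** 140 / (1 − 0.07) = 150.5, so 151. Rounding up arm by arm gives 44 + 33 + 33 + 44 = 154. The stated 152 is consistent with this.

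**Arm sizes at 152.** 152 × 4/14 = 43.4 and 152 × 3/14 = 32.6, so about 43 / 33 / 33 / 43.
- Assigned to LDP: 43.4 + 32.6 = 76 of 152 (50%).
- LDP-free contrast in the four-arm table: Nyxol alone v Placebo alone, about 33 v 43, together 76.
- Pre-Treatment 2 table pooled by Treatment 1: 76 v 76, together 152.

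**Precision.** Half-width = 1.96 × √[p₁(1 − p₁)/n₁ + p₂(1 − p₂)/n₂].

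| Assumed rates | 33 v 43 | 76 v 76 |
|---|---|---|
| 31.6% v 5.0% | 1.96 × √(0.2161/33 + 0.0475/43) = 17.1 points | 1.96 × √(0.2161/76 + 0.0475/76) = 11.5 points |
| 16% v 5% | 1.96 × √(0.1344/33 + 0.0475/43) = 14.1 points | 1.96 × √(0.1344/76 + 0.0475/76) = 9.6 points |

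The pooled interval is about a third narrower: 1 − 11.5/17.1 = 33% and 1 − 9.6/14.1 = 32%.

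**Seeing an uncommon event.** For an assumed 2% rate on Nyxol, the chance of at least one case is 1 − 0.98³³ = 49% with 33 subjects and 1 − 0.98⁷⁶ = 78% with 76.

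**Dilution of the LDP contrast.** Suppose a share b of both Nyxol arms has a given event before Visit 2, LDP independently causes the same event in a share r, and nothing else happens later. Counting once per subject, the whole-study difference is [b + (1 − b)r] − b = (1 − b)r. With b = 16% the contrast shows 84% of r; with b = 31.6% it shows 68%.

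**Adding arms in the whole-study table is no substitute.** Of Nyxol subjects 4/7 = 57% are assigned LDP, but of Placebo subjects 3/7 = 43%. An LDP-caused rate r adds r × (4/7 − 3/7) = r/7 to the Nyxol − Placebo difference: 1.4 points at an assumed r of 10%, 4.3 points at 30%.

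**The case against.** The strongest defence is that the arms are randomised. Nyxol + LDP and Nyxol alone share the same exposure before Visit 2, so early events balance in expectation and the contrast between them still isolates LDP; likewise for the two Placebo arms. A whole-study table by regimen is a recognised summary, and the objective on components already has a Nyxol-alone and an LDP-alone arm. This stands. A reader might infer that the planned tables are biased, or that they conceal LDP's effect; the design does not support that. What remains is dilution, noise and poor attribution.

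A reader might also infer that the same comparison is being run on half its sample. It is not: the pooled table stops at Treatment 2, whereas the four-arm table runs to the last visit. Nor would 43 v 43 (Nyxol + LDP v Placebo alone) or 33 v 33 (Nyxol alone v Placebo + LDP) serve as Nyxol-against-Placebo comparisons, since both are confounded with LDP.

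Other points that stand:
- No AE test or interval is planned. SAP Section 10.1 gives counts and percentages, and Section 7.4.1 makes safety p-values descriptive, so the half-widths only measure information.
- The 31.6% and 5.0% come from subjects with open-angle glaucoma or ocular hypertension dosed for 14 days, not presbyopes after 3 to 4 doses.
- Section 12.1 is redacted. It cannot be said that no by-period table exists, only that Section 10.1 lists none. Section 7.4.1 permits expanded descriptive categories but does not commit to them.
- Safety uses actual treatment, so a subject who leaves before Visit 2 need not be counted under LDP. The SAP does not say where that subject goes.
- Start dates are recorded and all AEs are listed by subject, so the split can be derived. Listings give no rates by period, however.

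**Conclusion.** The point holds as a cheap improvement to a descriptive safety analysis, not as an error that invalidates one. On the readable text, TEAEs from before Treatment 2 are counted in LDP columns for subjects who go on to receive LDP, and the Nyxol-against-Placebo contrast that the SAP makes for DCNVA at 0 minutes has no TEAE counterpart. The gain is 76 v 76 subjects in a shorter window against about 33 v 43 free of LDP, with a half-width about a third smaller under either assumed pair of rates. The sample sizes follow from the 4:3:3:4 allocation and 152 randomised; the half-widths rest on assumed rates and are illustrations only. The conclusion is subject to the redaction of Section 12.1.

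**What to change.** Keep the whole-study tables and add two to SAP Section 10.1:

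1. TEAEs with onset before Treatment 2, pooled Nyxol v pooled Placebo, in the Safety Population.
2. TEAEs with onset or worsening at or after Treatment 2, by the four arms, with subjects who reached Treatment 2 at Visit 2 as denominator.

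State two rules with them:

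- **Onset on the Visit 2 day.** Section 10.1 classifies TEAEs by date, which cannot place an event before or after Time 0. Use onset time, or the assessment timepoint at which the event was reported; if neither is known, assign the event to the period after Treatment 2. Section 7.3.2.1 fills a missing start day with the first-dose day when month and year match, which would put the event before Treatment 2. Say which convention governs these tables.
- **Subjects who leave before Visit 2.** Say in which column of the whole-study tables they are counted. They belong in table 1 under their Treatment 1 and not in table 2.

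The cost is two more descriptive tables and one onset-time rule. Start dates are already collected (Protocol Section 8.3); whether onset time is recorded for the Visit 2 day should be checked on the case report form.

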## ***8.3. Adverse Events and Serious Adverse Events***

All AEs and SAEs that occur following consent and until the final study visit should be collected and recorded on the AE or SAE eCRF page. Only TEAEs will be summarized ([Section 8.3.1](#)).

All AEs/adverse reactions occurring during the study (i.e., once the subject has signed the informed consent) **must** be documented, regardless of the assumption of causal relationship, on the respective eCRF. All TEAEs/treatment-emergent adverse reactions must be documented from the time the subject receives the study medication until the subject's participation in the study has been completed. If a subject has ongoing AEs/adverse reactions at the time of study completion or discontinuation from the study, the ongoing AEs/adverse reactions **must** be followed up and provided appropriate medical care until the signs and symptoms have remitted or stabilized or until medical assessments have returned to acceptable or pre-study limits.

Documentation of AEs/adverse reactions includes start date and end date, severity, relationship to study medications, action(s) taken, seriousness, and outcome.

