- Drug withdrawn: An indication that a medication schedule was modified through termination of a prescribed regimen of medication.
- Not applicable: Determination of a value is not relevant in the current context.
- Unknown: Not known, not observed, not recorded, or refused.

Additional other action taken:

- Concomitant medication
- Hospitalization

Outcome of an AE is coded as:

- Fatal: The termination of life as a result of an AE.
- Not recovered/not resolved: One of the possible results of an AE outcome that indicates that the event has not improved or the subject has not recuperated.
- Recovered/resolved: One of the possible results of an AE outcome that indicates that the event has improved or the subject has recuperated.
- Recovered/resolved with sequelae: One of the possible results of an AE outcome where the subject recuperated but retained pathological conditions resulting from the prior disease or injury.
- Recovering/resolving: One of the possible results of an AE outcome that indicates that the event is improving.
- Unknown: Not known, not observed, not recorded, or refused.

In previous clinical studies of Nyxol, the most frequently reported AE was conjunctival hyperemia.

In the present study, any increase of 2 units in conjunctival hyperemia between consecutive timepoints is considered an AE.

Investigators are cautioned to use the appropriate verbatim term on the AE form to describe this observation:

- Redness related to instillation that is transient (i.e., is no longer present 2 hours after instillation) = “conjunctival erythema upon instillation.”
- Redness that is NOT transient (i.e., is present 2 hours after instillation) = “conjunctival hyperemia.”

**Expedited reporting of serious and unexpected adverse events:** All SAEs (related and unrelated) will be recorded following subject signature of the informed consent and until the Safety Follow-Up Call (Visit 3/Day 5). Any SAEs “suspected” to be related to the study medication and discovered by the Investigator at any time **after** the study must be reported.

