### **9.3.6. Analysis of Safety**

Safety will be assessed using the SP with subjects included in the treatment arm they actually received, regardless of their randomized treatment. Observed case data will be used; no imputation will be performed for missing safety data. A statistical analysis of conjunctival hyperemia will be conducted as described below; otherwise, no statistical analysis of safety data will be performed.

For HR and BP, Baseline is defined as the Screening value. HR and BP values and change from Baseline in the values will be summarized by treatment arm and timepoint (Visit 1 and Visit 2).

Observed values and change from Baseline (Visit 1) in conjunctival hyperemia at each timepoint (Visit 1 at 0 and 1 hour, and Visit 2 at 0 minutes, 30 minutes, 1 hour, 2 hours, 3 hours, 4 hours, and 6 hours), will be summarized for the study eye and fellow eye. Treatments will be compared using the same ANCOVA model proposed for the continuous secondary efficacy endpoints.

For IOP, Baseline is defined as the Screening value. Observed values and change from Baseline in IOP at each timepoint (Visit 1 and Visit 2) will be summarized for the study eye and the fellow eye.

Ocular tolerability values will be summarized by treatment arm at each timepoint (Visit 1 and Visit 2).

Verbatim descriptions of AEs will be coded using MedDRA. Only TEAEs (those that occur after the first dose of study medication *or increasing in severity after initiation of study medication*) will be summarized. TEAEs and SAEs will be summarized by treatment group, by system organ class (SOC), severity, and relationship to study medication. Deaths, withdrawal from study medication due to AEs, and withdrawal from the study due to AEs will each be summarized by treatment group. Note that in MedDRA, ocular events are coded to the SOC of “special senses.” Thus, using SOC in the summaries will provide a separation of ocular and non-ocular AEs.

All safety data will be provided in by-subject listings.

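### Ocular and non-ocular adverse events are split by MedDRA system organ class alone, under two different class names, and the plan does not show that expected instillation reactions fall in that class

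*SAP*

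**What the plan says.** SAP 10.1 states the dictionary ("AEs will be coded using MedDRA, Version 23.1"), gives Eye Disorders as the SOC for ocular events, and concludes: "Thus, using SOC in the summaries will provide a separation of ocular and non-ocular adverse events".

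Protocol 9.3.6 draws the same conclusion ("Thus, using SOC in the summaries will provide a separation of ocular and non-ocular AEs") from a different premise. Its sentence beginning "Note that in MedDRA, ocular events are coded to the SOC of" ends by naming special senses. The only MedDRA version that the protocol names is 23.1 (section 9.3.4), the same as in SAP 7.3.5 and 10.1. SAP 3.3 lists the SAP's changes from the protocol. It does not list this one, and it says the analyses are otherwise consistent.

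No other means of separation is stated. The tables itemized in SAP 10.1 are by SOC and preferred term, some with relationship or severity added, and none is described as ocular. On what is recorded for each event, protocol 8.3 says: "Documentation of AEs/adverse reactions includes start date and end date, severity, relationship to study medications, action(s) taken, seriousness, and outcome". No eye or site item appears there. By contrast, SAP 8.4 summarizes ocular and non-ocular medical history separately.

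The protocol expects reactions when drops are instilled:
- For the earlier 14-day Nyxol trial, section 2.2 names as the most frequent events "conjunctival hyperemia and burning on instillation (each seen in 16% of subjects treated with Nyxol".
- For pilocarpine, section 2.2 names browache and stinging in the eye.
- Section 8.3.1 prescribes one verbatim term, conjunctival erythema upon instillation, for "Redness related to instillation that is transient (i.e., is no longer present 2 hours after instillation", and another, conjunctival hyperemia, for redness still present at 2 hours.

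**The concern.** A split by SOC is only as good as its premise that all eye events sit in one class. Two documents that name two classes for one dictionary cannot both be right, which suggests that the premise was not checked. The terms most likely to test it are the reactions expected here. Each describes a response to the act of dosing or a pain around the eye, and nothing in either document says where such terms code. Whether browache counts as ocular at all is a decision that the plan leaves to the dictionary.

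Adverse events are one of three primary safety measures (protocol 4.1). Ocular safety of the combination and of each component is a stated objective (protocol 3, SAP 4.1). The figure that a reader will look for is the proportion of subjects with at least one ocular event, by arm. If some eye reactions were counted as non-ocular, that proportion would be too low.

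**Working it through.** **1. The premise, side by side.** Protocol 9.3.6: ocular events go to special senses. SAP 10.1: ocular events go to Eye Disorders. The conclusion is the same and the dictionary is the same. At least one sentence is wrong. The difference in name does not by itself move any event between tables, since one coded data set is tabulated either way.

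**2. Where the expected terms code.** The documents give no preferred term or SOC for burning on instillation, stinging, browache or conjunctival erythema upon instillation. The number coded outside the eye class therefore cannot be computed from them and is treated below as unknown.

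**3. The earlier trial's figures (protocol 2.2; Nyxol n = 19, placebo n = 20).**
- Burning on instillation: 3/19 = 15.8%, stated as 16%.
- Any treatment-emergent event (TEAE): 6/19 = 31.6% on Nyxol and 1/20 = 5.0% on placebo, as stated.

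**4. Scale in this trial.**
- Allocation is 4:3:3:4 with about 152 randomized, so Nyxol subjects number 152 × (4 + 3)/14 = 76.
- Expected with burning on instillation: 76 × 3/19 = 12.
- The exact (Clopper-Pearson) 95% interval for 3/19 runs from the 2.5% point of Beta(3, 17), 3.4%, to the 97.5% point of Beta(4, 16), 39.6%. Times 76, this is 2.6 to 30.1, or about 3 to 30 subjects.
- The documents give no rate for pilocarpine reactions, so these are not included.

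**5. Effect on the ocular count.** Let k be the number of subjects whose only eye events code outside the eye class. The SOC-based count is the true count minus k. With about 12 subjects having the reaction, k can be anything from 0 to 12 on this source alone. As an illustration, suppose that all 6 Nyxol subjects with a TEAE in the earlier trial had an eye event, and that k of the 3 with burning had no other. The SOC-based ocular rate is then (6 − k)/19: 31.6%, 26.3%, 21.1% or 15.8% for k = 0, 1, 2 or 3.

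**6. Direction.** The No Treatment arms receive no second drop, so pilocarpine instillation reactions can arise only in the two LDP arms. In the earlier trial TEAEs were far more common on Nyxol (31.6% against 5.0%). Any loss would therefore fall mainly on the active arms. The placebo rate of burning is not given, so some loss there is possible.

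**7. Whether the tables allow repair.** SAP 10.1 counts a subject once at each level of tabulation. One subject may appear in several preferred-term rows, so rows from different SOCs cannot be added to give the number of subjects with at least one ocular event. That number would have to be derived again from subject-level data.

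**The case against.** The strongest reply is that misclassification is not in evidence. It needs eye reactions to code outside the eye class, and the documents map no term to any class. That stands: the understatement is conditional, and zero loss is within the range.

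Three stronger readings are tempting and are not supported:
- A reader might infer that two subjects with the same red eye will be tabulated in different SOCs according to whether the redness lasted 2 hours. Protocol 8.3.1 prescribes two verbatim terms but assigns neither a preferred term nor an SOC.
- A reader might infer that the conflict in SOC names itself misplaces events. It does not (step 1).
- A reader might add the earlier trial's hyperemia reports to those at risk. The protocol does not call them transient, and its term for lasting redness is conjunctival hyperemia.

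It can also be said that little would be hidden. Every preferred term is shown by arm, every event is listed, and hyperemia, tolerability and IOP are analyzed by eye. This is true of individual terms but not of the subject-level ocular count (step 7). The post-baseline times for hyperemia and tolerability in SAP 10.3 and 10.4 run from 0 minutes to 6 hours at Visit 2. Evening drops taken at home have no scheduled assessment of their own, so adverse event reports are the main source for reactions to them. A better flag would not improve that ascertainment; it would only classify correctly what is reported.

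Finally, the list of planned tables is redacted, the case report form is not in the documents, and the field list in protocol 8.3 need not be complete. A separate ocular table or an eye-affected field may exist. Even so, the rule in the readable text is SOC, and that rule would still need correcting.

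**Conclusion.** The point holds as a weakness in the definition, not as a demonstrated error in counts. SOC is the only stated basis for the ocular split, its premise is stated in two incompatible ways, and it is unverified for the reactions most expected here. If all eye terms code to one class, nothing is lost. If some do not, the subject-level ocular TEAE rate is understated, mainly in the active arms. For burning on instillation alone, about 12 of 76 Nyxol subjects would have the reaction (about 3 to 30), with none to all of them affected.

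This rests on two assumptions. One is that the rate from a 14-day trial with 19 Nyxol subjects carries over to 3 to 4 evening doses; the interval covers sampling error but not that difference in exposure. The other is that some terms code outside the eye class, which must be checked in the coding. No efficacy result, power or significance level is affected.

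**What to change.** 1. Correct the SOC sentence in protocol 9.3.6 and SAP 10.1 so that both agree with the dictionary version used, and list the change in SAP 3.3.
2. In SAP 10.1, stop defining the split by SOC. Define an ocular TEAE by the eye-affected field on the AE form if there is one. Otherwise define it by a list of preferred terms classed as ocular whatever their SOC, fixed in masked review before database lock. The review should decide explicitly on burning, stinging, browache and both redness terms.
3. Report the number and percentage of subjects with at least one ocular TEAE, and with at least one non-ocular TEAE, by arm on that flag. Keep the SOC and preferred-term tables as planned.

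The two redness terms can stay separate, as the protocol intends; the flag only has to count both as ocular.

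The cost is a few sentences, one derived variable and a short masked review. The reported ocular rate may be higher than under the SOC rule. If every eye term already codes to one class, the results do not change.
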